10.6. Appendix 6: Contraceptive Guidance and Collection of Pregnancy Information

Definitions:

WOCBP

A woman is considered fertile following menarche and until becoming postmenopausal unless permanently sterile (see below).

Women in the following categories are not considered WOCBP:

1. Premenarchal
2. Premenopausal female with 1 of the following:
 - Documented hysterectomy
 - Documented bilateral salpingectomy
 - Documented bilateral oophorectomy

[figure not shown]
Note: Documentation can come from the site personnel's review of the participant's medical records, medical examination, or medical history interview.
3. Postmenopausal female
 - A postmenopausal state is defined as no menses for 12 months without an alternative medical cause. A high FSH level in the postmenopausal range may be used to confirm a postmenopausal state in women not using hormonal contraception or HRT. However, in the absence of 12 months of amenorrhea, a single FSH measurement is insufficient.
 - Females on HRT and whose menopausal status is in doubt will be required to use one of the nonestrogen hormonal highly effective contraception methods if they wish to continue their HRT during the study. Otherwise, they must discontinue HRT to allow confirmation of postmenopausal status before study enrollment.

Contraception Guidance:

Female Participants

Female participants of childbearing potential are eligible to participate if they agree to use a highly effective method of contraception consistently and correctly as described in [Table 10-1](#).

[figure not shown]
██████████
AGN-190584

Approval Date: 06-Mar-2020

██████████

██████████
AGN-190584

[figure not shown]

Approval Date: 06-Mar-2020

[Redacted]

[figure not shown]
AGN-190584

Approval Date: 06-Mar-2020

[Redacted]

[figure not shown]
██████████
AGN-190584

Approval Date: 06-Mar-2020

██████████

██████████
AGN-190584

[figure not shown]
Approval Date: 06-Mar-2020

██████████

[REDACTED]

Protocol 1883-302-013

AGN-190584

[figure not shown]
Approval Date: 06-Mar-2020

[REDACTED]

[Redacted]

Protocol 1883-302-013

[figure not shown]
AGN-190584

Approval Date: 06-Mar-2020

[Redacted]

██████████
AGN-190584

[figure not shown]

Approval Date: 06-Mar-2020

[REDACTED]
AGN-190584

[figure not shown]
Protocol 1883-302-013

Approval Date: 06-Mar-2020

[REDACTED]

██████████
AGN-190584

[figure not shown]
Approval Date: 06-Mar-2020

[Redacted]

Protocol 1883-302-013

[figure not shown]
AGN-190584

Approval Date: 06-Mar-2020

[Redacted]

[figure not shown]
██████████
AGN-190584

Approval Date: 06-Mar-2020

[figure not shown]
██████████
AGN-190584

Approval Date: 06-Mar-2020

██████████
AGN-190584

Approval Date: 06-Mar-2020

[REDACTED]

Protocol 1883-302-013

AGN-190584

[REDACTED]

Approval Date: 06-Mar-2020

[REDACTED]

[REDACTED]

Protocol 1883-302-013

[figure not shown]
AGN-190584

[REDACTED]

Approval Date: 06-Mar-2020

[REDACTED]

██████████
AGN-190584

[figure not shown]
Approval Date: 06-Mar-2020

██████████

[REDACTED]

Protocol 1883-302-013

AGN-190584

[figure not shown]

Approval Date: 06-Mar-2020

[REDACTED]

██████████
AGN-190584

10.8. Appendix 8: Patient Reported Outcomes Questionnaires, Descriptions, and Instructions

[figure not shown]
Approval Date: 06-Mar-2020

██████████
AGN-190584

Approval Date: 06-Mar-2020

██████████
AGN-190584

[figure not shown]
Approval Date: 06-Mar-2020

██████████
AGN-190584

Approval Date: 06-Mar-2020

[figure not shown]
██████████
AGN-190584

Approval Date: 06-Mar-2020

[figure not shown]
██████████
AGN-190584

Approval Date: 06-Mar-2020

[figure not shown]
██████████
AGN-190584

Approval Date: 06-Mar-2020

[figure not shown]
██████████
AGN-190584

Approval Date: 06-Mar-2020

[figure not shown]
██████████
AGN-190584

Approval Date: 06-Mar-2020

██████████
AGN-190584

[figure not shown]
Approval Date: 06-Mar-2020

██████████
AGN-190584

[figure not shown]
Approval Date: 06-Mar-2020

AGN-190584

[figure not shown]
Approval Date: 06-Mar-2020

AGN-190584

[figure not shown]
Approval Date: 06-Mar-2020

██████████
AGN-190584

Approval Date: 06-Mar-2020

[figure not shown]
██████████
AGN-190584

Approval Date: 06-Mar-2020

██████████
AGN-190584

[figure not shown]
Approval Date: 06-Mar-2020

[REDACTED]
AGN-190584**10.8.2. Near Vision Presbyopia Task-based Questionnaire****Near Vision Presbyopia Task-based Questionnaire (NVPTQ)**

[figure not shown]
Instructions: This questionnaire includes 12 questions on four reading tasks that you are about to complete.

You will be asked to read text from the following examples:

- Paragraph from a book
- Newspaper article
- Menu
- Nutrition label

[figure not shown]
██████████
AGN-190584

Approval Date: 06-Mar-2020

[figure not shown]
██████████
AGN-190584

Approval Date: 06-Mar-2020

[figure not shown]
██████████
AGN-190584

Approval Date: 06-Mar-2020

[figure not shown]
██████████
AGN-190584

Approval Date: 06-Mar-2020

[figure not shown]
██████████
AGN-190584

Approval Date: 06-Mar-2020

██████████

[figure not shown]
██████████
AGN-190584

Approval Date: 06-Mar-2020

██████████

[figure not shown]
██████████
AGN-190584

Approval Date: 06-Mar-2020

██████████

[figure not shown]
██████████
AGN-190584

Approval Date: 06-Mar-2020

[figure not shown]
██████████
AGN-190584

Approval Date: 06-Mar-2020

[figure not shown]
██████████
AGN-190584

Approval Date: 06-Mar-2020

██████████

[figure not shown]
██████████
AGN-190584

Approval Date: 06-Mar-2020

[figure not shown]
██████████
AGN-190584

Approval Date: 06-Mar-2020

██████████
AGN-190584

[figure not shown]

Approval Date: 06-Mar-2020

[REDACTED]
AGN-190584

AGN-190584

### SAP Version History

This Statistical Analysis Plan (SAP) for study 1883-302-013 is based on the [protocol](#) dated March 06, 2020.

SAP Version History Summary			
SAP Version	Approval Date	Change	Rationale
1		Not Applicable	Original version

AGN-190584

## **1. Introduction**

This Statistical Analysis Plan (SAP) provides a technical and detailed elaboration of the statistical analyses of the efficacy and safety data as outlined and specified in the final [protocol amendment 1](#) of study 1883-302-013 (dated 06 March 2020). Specifications of tables, figures, and data listings are contained in a separate document. The SAP for health economics data will be prepared separately.

AGN-190584

**Objectives and Endpoints**

The objectives of this study are to evaluate the efficacy and safety of AGN-190584 when administered bilaterally, once daily for 30 days in participants with presbyopia. Details of the study objectives and corresponding endpoints are described in the table below:

Objectives	Endpoints

To evaluate the efficacy of AGN-190584 when administered bilaterally, once daily for 30 days in participants with presbyopia.
	
 
• Mesopic and photopic, high contrast DCNVA for each eye and binocularly
 
• Mesopic and photopic, high contrast DCIVA for each eye and binocularly
 
 

 
 
• PRO questionnaires:               
 
○ Mesopic and Photopic NVPTQ
 
○ PICQ
 
 
 
 

To evaluate the safety and tolerability of AGN-190584 when administered bilaterally, once daily for 30 days in participants with presbyopia
	
 
• AEs
 
• Photopic and mesopic high contrast CDVA for each eye and binocularly
 
• Near Contrast sensitivity
 
• Vital signs (blood pressure and heart rate)
 
• Study drug tolerability and drop comfort assessments
 
• Temporal/supraorbital headache VAS
 
• IOP
 
• Slit-lamp biomicroscopy
 
• Manifest refraction
 
• Dilated funduscopy examination
 

AGN-190584

[figure not shown]
## 1.1. Study Design

Study 1883-302-013 is a multicenter, double-masked, randomized, vehicle-controlled, parallel group, phase 3 study evaluating the efficacy and safety of AGN-190584 (1.25% pilocarpine) dosed once daily, bilaterally, over a period of 30 days in participants with presbyopia. The study population will consist of adult male and female participants with objective and subjective evidence of presbyopia. Approximately 200 participants per group will be randomized.

Participants will be randomized in a 1:1 ratio to receive either AGN-190584 or vehicle dosed once daily, in each eye, for 30 days. This randomization will be stratified by age (2 groups:  $\leq 50$  years and  $> 50$  years), baseline binocular DCNVA (2 groups: 20/40 to 20/60 inclusively, and worse than 20/60), iris color (brown and non-brown), and emmetropes/non-emmetropes. This study consists of the following visits: screening (Days -30 to -1), Day 1 (baseline), and Days 3, 7, 14, and 30.

Study interventions, either AGN-190584 or vehicle will be administered as topical eye drop once daily. Following the study schema (Figure 1-1), study intervention will be administered by designated site personnel on visit days and at home by the participant in-between office visits, ideally prior to starting their day. On the day before office visits, the study intervention must be administered no less than 16 hours before the scheduled visit time.

[figure not shown]
**Figure 1-1 Study Schema**

The schedule of activities for Study 1883-302-013 is presented in [Table 1-1](#) and [Table 1-2](#).

[figure not shown]
AGN-190584

**Table 1-1**      **Schedule of Visits and Procedures: Screening to Visit 3**

[figure not shown]
A large black rectangular redaction box covers the entire content area of the page, obscuring the table data.

[figure not shown]
AGN-190584

[figure not shown]
AGN-190584

AGN-190584

[figure not shown]

AGN-190584

[figure not shown]

AGN-190584

[figure not shown]
**Table 1-2**      **Schedule of Visits and Procedures: Visit 4 to Visit 5/Early Exit**

The content of the table is completely redacted with a large black rectangular block covering the entire area.

AGN-190584

AGN-190584

AGN-190584

## **2. Statistical Hypotheses**

For the primary efficacy analysis, the null hypothesis is that there is no difference between AGN-190584 ophthalmic solution and vehicle dosed bilaterally, once daily for 30 days in the proportion of participants gaining 3 lines or more from baseline in mesopic, high contrast, binocular DCNVA without losing more than 5-letters of mesopic, high contrast, binocular CDVA with the same refractive correction at Day 30, Hour 3. The alternative hypothesis is that there is a difference between AGN-190584 ophthalmic solution and vehicle.

For the key secondary efficacy analysis, the null hypothesis is that there is no difference between AGN-190584 ophthalmic solution and vehicle dosed bilaterally, once daily for 30 days in the proportion of participants gaining 3 lines or more from baseline in mesopic, high contrast, binocular DCNVA at Day 30, Hour 6. The alternative hypothesis is that there is a difference between AGN-190584 ophthalmic solution and vehicle.

The hypotheses will be tested using chi-square tests at a significance level of 5%.

AGN-190584

### **3. Sample Size Determination**

The primary efficacy parameter is the proportion of participants gaining 3 lines or more from baseline in mesopic, high contrast, binocular DCNVA without losing more than 5-letters of mesopic, high contrast, binocular CDVA with the same refractive correction at Day 30, Hour 3. The key secondary efficacy parameter is the proportion of participants gaining 3 lines or more from baseline in mesopic, high contrast, binocular DCNVA at Day 30, Hour 6. The sample size calculation is based on the key secondary efficacy parameter.

The vehicle group intervention effect and AGN-190584 effect are assumed to be 8.8% and 18.4%, respectively, as observed in the Phase 3 study 1883-301-013. Two hundred (200) participants will be required in each study intervention group to detect the above difference with a power of 80% or greater at the 2-sided 5% significance level.

AGN-190584

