### **5.4.3. Multiplicity Adjustment**

[figure not shown]
The graphical procedure displayed in [Figure 5-1](#) will be employed to control the overall familywise error rate at  $\alpha=0.05$  for the following hypotheses testing. Let  $1r_y$ ,  $2r_y$ ,  $H1$ ,  $H2$ ,  $H3$ ,  $H4$ ,  $H5$ ,  $H6$ ,  $H7$ ,  $H8$ ,  $H9$ ,  $H10$ , and  $H11$  represent the treatment effect comparisons of AGN-190584 with vehicle. Details of the hypotheses and corresponding efficacy parameters are described in [Table 5-1](#).

AGN-190584

Table 5-1 Hypotheses and Corresponding Efficacy Parameters

Hypothesis	Efficacy Parameter
1yr	Proportion of participants gaining 3-lines or more in mesopic, high contrast, binocular, DCNVA without losing more than 5-letters of mesopic, high contrast, binocular CDVA with the same refractive correction at Day 30, Hour 3
2ry	Proportion of participants gaining 3-lines or more in mesopic, high contrast, binocular, DCNVA at Day 30, Hour 6
H1	Proportion of participants gaining 3-lines or more in mesopic, high contrast, binocular, DCNVA at Day 30, Hour 8
H2	Change from baseline in mesopic, high contrast, binocular DCNVA letters at Day 30, Hour 0.5
H3	Proportion of participants achieving 20/40 or better in photopic, high contrast, binocular, DCNVA at Day 30, Hour 1
H4	Change from baseline in photopic, high contrast, binocular DCIVA letters at Day 30, Hour 3
H5	Change from baseline in Mesopic NVPTQ Performance score at Day 30, Hour 3
H6	Proportion of participants gaining 3-lines or more in mesopic, high contrast, binocular, DCNVA at Day 30, Hour 10
H7	Change from baseline mesopic, high contrast, binocular DCNVA letters at Day 30, Hour 0.25
H8	Proportion of participants achieving 20/40 or better in photopic, high contrast, binocular, DCNVA at Day 30, Hour 3
H9	Change from baseline in Mesopic NVPTQ Satisfaction score at Day 30, Hour 3
H10	Change from baseline in PICQ Coping score at Day 30, Hour 3
H11	Change from baseline in PICQ Impact score at Day 30, Hour 3

AGN-190584

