**Figure 5-1 Graphical Testing Procedure**

Specifically, 2ry, H2, H3, H4 and H5 will be tested at  $\alpha=0.01$  separately. If 2ry, H2, H3, H4 or H5 is rejected, H7, H8 or H9 will then be tested. If H9 is rejected, H10 and H11 will then be tested. H1 and H6 will be tested only if all other endpoints are significant.

AGN-190584

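### The 80% power for the key secondary endpoint assumes a 5% test, but the SAP tests it at 0.01, where 200 per group gives about 59%

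*SAP*

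**What the plan says.** SAP Section 3 names the endpoint that drives the sample size: "The sample size calculation is based on the key secondary efficacy parameter". It gives the planning rates ("The vehicle group intervention effect and AGN-190584 effect are assumed to be 8.8% and 18.4%, respectively"), taken from the first Phase 3 study, and asks for 200 per arm. The claim attached to that number is that it will "detect the above difference with a power of 80% or greater at the 2-sided 5% significance level". Protocol 9.2 makes the same statement.

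SAP 5.4.3 sets up a graphical procedure that "will be employed to control the overall familywise error rate at" 0.05. The text under Figure 5-1 reads: "2ry, H2, H3, H4 and H5 will be tested at $\alpha=0.01$ separately". Table 5-1 identifies 2ry as the same key secondary endpoint. The text then describes testing H7, H8 or H9 after a rejection in that first set, H10 and H11 after H9, and H1 and H6 only if everything else is significant.

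SAP Section 2 states hypotheses for the primary and the key secondary only, and closes: "The hypotheses will be tested using chi-square tests at a significance level of 5" per cent. SAP 5.1 sets a general 2-sided 5% level that applies unless stated otherwise, and sends the secondary endpoints to Figure 5-1.

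**The concern.** Power was calculated at one significance level, and the endpoint will be tested at another that is five times stricter. Amendment 1 moved to one-level gatekeeping, so the other secondary endpoints no longer wait for the key secondary. Protocol 9.4.1.3 left the multiplicity procedure to the SAP. The SAP then divided 0.05 equally over five hypotheses but kept the 5% power statement.

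Two things are at stake. First, this is the only power figure in the plan, and it accompanies an enlargement from 300 to 400 participants that was made to raise power. Second, SAP Section 2 and SAP 5.4.3 give different thresholds for the endpoint on which the trial was sized. A key secondary p-value of 0.03, for example, is significant under one section and not under the other.

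**Working it through.** **Inputs**
- Response rates 8.8% and 18.4%, 200 per group (SAP 3; Protocol 9.2), 1:1 allocation (SAP 1.1).
- Chi-square test, pooled variance, no continuity correction (SAP 5.3.2, applied to the key secondary by SAP 5.4.1).
- No allowance for dropout; missing data count as non-response (SAP 5.1).
- Level 0.05 for sizing (SAP 3) and 0.01 for testing (SAP 5.4.3).

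**Formula**

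Power = Φ((d − z·SE0)/SE1), where z is the 2-sided critical value.
- d = 0.184 − 0.088 = 0.096
- Pooled rate = (0.088 + 0.184)/2 = 0.136
- SE0 = √(2 × 0.136 × 0.864/200) = 0.03428
- SE1 = √((0.088 × 0.912 + 0.184 × 0.816)/200) = 0.03394

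**Reproducing the plan's figure (level 0.05)**

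Φ((0.096 − 1.960 × 0.03428)/0.03394) = Φ(0.849) = 80.2%. Exact binomial enumeration gives 81.0%. The smallest n for 80% is 199 per group. The stated 80% with 200 per group is therefore correct for a 5% test.

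**At the level the SAP assigns (0.01)**

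Φ((0.096 − 2.576 × 0.03428)/0.03394) = Φ(0.227) = 59.0%. Exact enumeration gives 59.7%. Reaching 80% would take 297 per group. Equivalently, with 200 per group, 80% power at 0.01 requires 20.9% responding against 8.8%, not 18.4%.

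**If Figure 5-1 returned some alpha to 2ry**

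| Level reaching 2ry | Power, 200 per group |
|---|---|
| 0.01 | 59% |
| 0.02 | 68% |
| 0.03 | 74% |
| 0.04 | 77% |
| 0.05 | 80% |

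**Size of the zone where Sections 2 and 5.4.3 disagree**

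Under the planning rates, the probability that p lies between 0.01 and 0.05 is 80.2% − 59.0% ≈ 21%.

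**Familywise error if Section 2 were followed for 2ry while H2 to H5 stayed at 0.01**

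At most 0.05 + 4 × 0.01 = 9%. If the tests are independent, 1 − 0.95 × 0.99⁴ = 8.7%. Either exceeds the stated 0.05.

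**The case against.** **The plan's arithmetic is not wrong.** True: Section 3 states its level and the figure reproduces. The defect is a mismatch between the level used for sizing and the level used for testing. The 80% still does not describe the test that will be done.

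**Figure 5-1 may return alpha to the key secondary.** It is not shown in the copy reviewed, and the text gives no transfer weights, so 59% is the power at the initial level. But the written description only passes alpha onward. Even with a return path, 80% would need the full 0.05 to reach 2ry. That would depend on rejecting other hypotheses, and the sample-size text states no such condition.

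**The more specific rule governs.** SAP 5.1 allows exceptions to 5% and points to Figure 5-1, so a reader of the whole SAP would probably use 0.01. This is a fair reading, and it makes the conflict with Section 2 easier to settle. The 9% familywise error would arise only if Section 2 were taken literally; 5.4.3 followed as written respects 0.05. But Section 2 names the key secondary and carries no qualifier, and this reading confirms that the power statement uses the wrong level.

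**The enlargement still raised power.** It did. Going from 150 to 200 per group moves power from 44% to 59% at 0.01, and from 68% to 80% at 0.05. What fails is the 80% target.

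**The protocol contained no 0.01 level.** Correct. The inconsistency arises in the SAP, and Protocol 9.2 carries it only because it states the same power.

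**Conclusion.** The concern holds. At the 0.01 level that the SAP assigns to the key secondary endpoint, 200 per group gives about 59% power (59.7% exact), not 80% or greater. This rests on the plan's own rates, 1:1 allocation, an uncorrected chi-square test and no alpha returned to 2ry. A return path in Figure 5-1 would place power between 59% and 80%.

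Two features of the plan can only lower the figure at 0.01. The key secondary is tested only if the primary succeeds, and SAP 5.1 excludes all participants from site 051 from the efficacy analyses. The number excluded is not given; an assumed 185 to 195 per group yields 54.7% to 57.6%.

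The conflict between SAP Section 2 and SAP 5.4.3 over the key secondary's threshold is real on the page and should be settled before unmasking. Familywise error is controlled if 5.4.3 is followed as written, and the primary test is unaffected.

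**What to change.** - **SAP Section 3 and Protocol 9.2:** state that, with 200 per group and 8.8% versus 18.4%, power for the key secondary is about 59% at its assigned 2-sided 0.01 level, and that 80% applies only to a 5% test. Note that this is before the primary gate and the site 051 exclusion. If Figure 5-1 does return alpha to 2ry, describe the path and give the power that goes with it.
- **SAP Section 2:** limit the 5% level to the primary hypothesis and refer to Figure 5-1 for the level of the key secondary.

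The cost is about two sentences of wording and a less favourable stated power. No test, endpoint or sample size changes. Changing Protocol 9.2 brings the usual amendment process; if the protocol is not reopened, the correction can be recorded in SAP Section 3 and Appendix 2.

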#### **4. Populations for Analysis**

Two analysis populations were defined for this study as follows:

- The intent-to-treat (ITT) population will consist of all randomized participants. The analysis using the ITT population will be based on the study intervention assigned.
- The safety population will consist of all participants who received at least 1 administration of study intervention. The analysis using the safety population will be based on the actual study intervention received.

AGN-190584

## 5. Statistical Analyses

### 5.1. General Considerations

- Efficacy endpoints will be analyzed using the ITT population, and the safety endpoints will be analyzed using the safety population.
- The baseline for efficacy and safety will be the last non-missing assessment prior to the first administration of study intervention. For participants who were randomized but not treated, the baseline value will be the assessment collected on or prior to the randomization date, whichever is later.
- The change from baseline values will be computed as the postbaseline value minus the baseline value.
- Continuous variables will be summarized by number of participants with observed values (n), mean, standard deviation (SD), median, 1st and 3rd quartiles (Q1, Q3), minimum (min), and maximum (max).
- Categorical variables will be summarized by number of participants with observed values or events (n), frequency count (n1) and percentage of participants with observed values or events.
- All statistical hypothesis tests will be performed at the 2-sided 5% significance level, unless stated otherwise. All confidence intervals will be at least 2-sided 95% confidence intervals.
- In general, statistical analyses will be performed using SAS version 9.4 or higher. MedDRA version 22.1 or higher will be used to code adverse events, biomicroscopy, and medical history. WHODRUG Enhanced B2 will be used to code medications.

To control the overall Type 1 error rate in the efficacy analysis, a gatekeeping testing strategy will be used. All secondary efficacy endpoints will be tested only if the primary efficacy endpoint is statistically significant and the testing procedures are described in the graphical procedure in [Figure 5-1](#).

For primary and key secondary analyses, participants with missing data will be regarded as non-responders. Analyses for other secondary efficacy endpoints will be based on observed data only.

Per confirmation of the site, DCNVA measurements were not conducted correctly for participants at investigator site 051 at screening visit and baseline visit (Day 1 Hour 0). In error, the participants were corrected for near vision rather than distance vision when these

AGN-190584

measurements were taken. Therefore, it is decided to exclude all participants from this site from efficacy analyses. These participants will be included in all safety analyses.

